- ADA Anti-drug antibody; AE Adverse event; C Cycle; CRT Chemoradiation therapy; CT Computed tomography; CTCAE Common Terminology Criteria for Adverse Events; ECG Electrocardiogram; ECOG Eastern Cooperative Oncology Group; EORTC European Organisation for Research and Treatment of Cancer; ePRO Electronic patient-reported outcome; EQ-5D-5L EuroQoL 5 dimension, 5 level health state utility index; HIV Human immunodeficiency virus; ICF Informed consent form; IP Investigational product (ie, durvalumab, tremelimumab, or placebo); LFT Liver function test; MRI Magnetic resonance imaging; PCI Prophylactic cranial irradiation; PD Progressive disease; PGIS Patient's Global Impression of Severity; PK Pharmacokinetic; PRO Patient-reported outcome; QLQ C30 30 Item core quality of life questionnaire; QLQ LC13 Lung cancer module; qXdays Every X days; qXw Every X weeks; RECIST Response Evaluation Criteria In Solid Tumors; SAE Serious adverse event; T3 Triiodothyronine; T4 Thyroxine; T8H Thyroid-stimulating hormone; WHO World Health Organization.

Table 2 Schedule of assessments for patients who have completed/discontinued treatment with durvalumab  $\pm$  tremelimumab therapy or placebo

					Time since	e last dose	of IP		
	Day (±3)			Week (	±1 week)			48 weeks and every	
Evaluation	30	8	12	16	24	32	40	8 weeks (±2 weeks) until study termination or death	For details, see Section
Physical examination (full)	X								8.2.2
Vital signs (temperature, respiratory rate, blood pressure, and pulse)	X								8.2.3
Weight	X	X	X						8.2.3
Pregnancy test a	X			•	As clinica	ally indica	ed		8.2.1
AE/SAE assessment	X	X	X						8.3
Concomitant medications	X	X	X						6.4
WHO/ECOG performance status	At time poi				nents; at Da ation of sub			1 week), and Week 12 erapy b	8.2.5
Second progression assessment c	progression)	(using the A patient'	patient's s s progressi	tatus at firs	st progression defined ac	on as the recording to	eference for local standa	ery 8 weeks for a second assessment of second and clinical practice and c progression, or death.	8.1.2
Subsequent anticancer therapy d and survival status e		X	X	X	X	X	X	X	8.1.2
Hematology	X	X	X						Table 9
Clinical chemistry	X	X	X						Table 8
TSH (reflex free T3 or free T4 f )	X	X	X						Table 8
Durvalumab PK assessment g			X						8.5
Tremelimumab PK assessmenth			X						8.5

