## 2.3.2.2 Durvalumab after completion of CRT

In the PACIFIC study (D4191C00001 [NCT02125461]), durvalumab treatment in patients with locally advanced, unresectable Stage III NSCLC who had recently completed CRT demonstrated a well-tolerated and manageable safety profile that was consistent with the established safety profile to date, with the exception of the events of pneumonitis/radiation pneumonitis (Antonia et al 2017, Antonia et al 2018). AEs were reported in 96.8% of patients who received durvalumab and 94.9% who received placebo; Grade 3 or 4 AEs were reported in 30.5% of patients who received durvalumab and 26.1% who received placebo. The most frequently reported Grade 3 or 4 AE was pneumonia (4.4% and 3.8%, respectively). SAEs were reported in 28.6% and 22.6% of patients, respectively, and deaths due to AEs occurred in 4.4% and 6.0% of patients, respectively. Pneumonitis and radiation pneumonitis were notable events in multiple AE categories. There was a numerical increase in these events in the durvalumab group over placebo (32.8% vs 23.5%, respectively, patients with pneumonitis or radiation pneumonitis of any grade), but most of these events were low grade and manageable. Grade 3 or 4 pneumonitis was reported in 3.4% and 2.1% of patients in the durvalumab and placebo groups, respectively. Clinically important CTCAE Grade 3 and above events were infrequent and balanced between the 2 groups. In addition to pneumonitis, the other adverse events of special interest (AESIs) and immune-mediated adverse events (imAEs) reported in the study were typical of the PD-1/PD-L1 class of immunotherapies and were generally manageable and/or reversible with appropriate treatment guidelines, which included the use of steroids or endocrine therapy, withholding durvalumab until the event resolved, or permanent discontinuation of durvalumab.

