#### 8.3.3 Follow-up of AEs and SAEs

After the initial AE/SAE report, the Investigator is required to proactively follow each patient at subsequent visits/contacts. All AEs and SAEs will be followed until resolution, stabilization, the event is otherwise explained, or the patient is lost to follow-up

Any AEs that are unresolved at the patient's last AE assessment or other assessment in the study are followed up by the Investigator for as long as medically indicated (this may be beyond the 90 days after the last dose of IP), but without further recording in the CRF. AstraZeneca retains the right to request additional information for any patient with ongoing AE(s)/SAE(s) at the end of the study, if judged necessary.

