#### 8.3.4 Adverse event data collection

The following variables will be collected for each AE:

- AE (verbatim)
- The date when the AE started and stopped
- The maximum CTCAE grade reported
- Changes in CTCAE grade (report only the maximum CTCAE grade for a calendar day)
- Whether the AE is serious or not
- Investigator causality rating against the IPs (yes or no)
- Action taken with regard to IPs
- Administration of treatment for the AE
- Outcome

In addition, the following variables will be collected for SAEs:

- Date the AE met criteria for SAE
- Date the Investigator became aware of the SAE
- Seriousness criteria
- Date of hospitalization
- Date of discharge
- Probable cause of death
- Date of death
- Whether an autopsy was performed
- Causality assessment in relation to study procedure(s)

- Causality assessment in relation to other medication, as explained in Section 8.3.5
- Description of the SAE

The grading scales found in the revised NCI CTCAE version 4.03 will be utilized for all events with an assigned CTCAE grading. For those events without assigned CTCAE grades, the recommendation in the CTCAE criteria that converts mild, moderate, and severe events into CTCAE grades should be used. A copy of the CTCAE version 4.03 can be downloaded from the Cancer Therapy Evaluation Program website (http://ctep.cancer.gov).

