A summary of all deaths will be provided with number and percentage of patients by treatment group in the FAS, categorized as:

- Total number of deaths (regardless of date of death)
- Death related to disease under investigation only as determined by the investigator.
- Death related to disease under investigation and an AE with outcome of death
 - AE onset prior to subsequent therapy, which includes AEs with an onset date (or pre-treatment AEs that increase in severity) on or after the date of first dose and up to and including 90 days following the last dose of study treatment, or

up to the date of initiation of the first subsequent therapy (whichever occurs first)

- AE onset after start of subsequent therapy, which includes AEs with onset date
 >90 days following the last dose of study treatment or AE start date ≥ the date of initiation of the first subsequent therapy (whichever occurs first)
- AE with outcome of death only
 - AE onset prior to subsequent therapy (as defined above)
 - AE onset after start of subsequent therapy (as defined above)
- Death after end of safety follow up period (last dose of study treatment + 90 days) and not due to AE or disease under investigation (*)
- Unknown reason for death
- Other deaths (deaths not captured in the earlier categories) e.g. death occurring after randomization but prior to receiving treatment and which is not related to disease under investigation

This summary will be produced twice; firstly, including all deaths and, secondly, including all deaths on-treatment or within 90 days of the last dose of study treatment. Hence the category marked (*) will only appear in the first summary.

Adverse events of special interest and possible interest

Preferred terms used to identify AESI and AEPI will be listed before DBL and documented in the Study Master File. Grouped summary tables of certain MedDRA preferred terms will be produced and may also show the individual preferred terms which constitute each AESI grouping. For each grouped term, the number (%) of patients experiencing any of the specified terms will be presented by maximum CTCAE grade. Time to onset of first AESI for each grouped term will also be produced. Groupings will be based on preferred terms provided by the medical team prior to DBL, and a listing of the preferred terms in each grouping will be provided.

Additional summaries of the above-mentioned grouped AE categories will include number (%) of patients who have:

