- At least one AESI/AEPI presented by outcome
- At least one AESI/AEPI leading to discontinuation of study medication

A summary of total duration (days) of AESI/AEPI will be provided for events which have an end date, and these may be supported by summaries of ongoing AESIs at death and, separately, at DCO.

Additionally, there will be several summaries of AESIs/AEPIs requiring concomitant treatment, and particularly the relationship of AESIs/AEPIs to the use of immunosuppressive agents (i.e. depicting which AESI/AEPI triggered immunosuppressive use), endocrine treatment and systemic corticosteroids, and, separately, to the use of systemic corticosteroids at high doses.

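### The AESI/AEPI duration summary covers only events with an end date, so it is biased short and cannot show persistent toxicity

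*SAP*

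**What the plan says.** SAP 4.2.13.1, under adverse events of special and possible interest, commits to this output: "A summary of total duration (days) of AESI/AEPI will be provided for events which have an end date". The sentence goes on to say that "these may be supported by summaries of ongoing AESIs at death and, separately, at DCO". That companion summary is optional and does not mention AEPIs.

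Three other provisions decide which events can have an end date:

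- SAP 4.1.3 imputes partial end dates but not wholly missing ones.
- Protocol Table 2 marks the row "AE/SAE assessment" at Day 30, Week 8 and Week 12 after the last dose and at no later time. Protocol 8.3.2 closes collection at 90 days.
- Protocol 8.3.3 keeps an event that is unresolved at the last assessment under medical follow-up, but the data trail stops: "this may be beyond the 90 days after the last dose of IP), but without further recording in the CRF".

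For the AESI groups the SAP also plans time to first onset. It plans no time-to-resolution analysis that keeps unresolved events in the denominator.

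**The concern.** An event enters the duration table only if it ends while someone is still recording. Events that outlast recording are the long ones, so removing them shortens the summary by construction. An event that never ends can never enter, however common such events are.

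The AESI list in protocol 8.3.12 includes endocrinopathies and neuromuscular toxicities, and its definition anticipates hormone replacement. How long immune events last is therefore a question that readers will bring to this output. Protocol 2.3.2.2 describes such events in an earlier study as "generally manageable and/or reversible with appropriate treatment guidelines". A short median duration printed without the number of events left out would invite the same description here, whether or not the data support it.

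**Working it through.** The plan states no figure for AESI duration, so there is none to reproduce. The check has two parts: a selection argument that needs no assumptions about size, and an illustration of size that does.

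**Selection.** Let D be the true duration of an event and W the recording time left at its onset: time from onset to last dose, plus the window after last dose. An end date exists when D ≤ W. The table reports the median of D given D ≤ W; the median over all events is a different quantity. A permanent event never satisfies D ≤ W. When permanence is unrelated to W, the reported median is therefore the same whatever the permanent share p.

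**Illustration.** 400,000 events per scenario. Assumptions, none of them planned values for AESIs:

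- time on treatment exponential, with median 10 or 15.4 months (the design's two PFS medians in protocol 9.2, used as stand-ins), capped at the 24-month treatment maximum;
- onset uniform over treatment;
- end dates recorded to 84 days (Week 12) after last dose;
- resolving events exponential with median m of 30, 60 or 120 days;
- permanent share p of 0%, 20% or 40%;
- no deaths.

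The all-event median t solves (1 − p)(1 − 2^(−t/m)) = 0.5, so t = m × log2{1/[1 − 0.5/(1 − p)]}. For p = 20% the multiplier is log2(1/0.375) = 1.415, giving 60 × 1.415 = 84.9 days. For p = 40% it is log2(6) = 2.585, giving 60 × 2.585 = 155.1 days.

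Paired entries are for the 10-month and 15.4-month treatment medians.

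| p | m (days) | No end date (%) | Median, events with end date | All-event median (formula) | Kaplan-Meier, all events |
|---|---|---|---|---|---|
| 0% | 30 | 3.5 / 2.6 | 29 / 29 | 30 | 30 / 30 |
| 0% | 60 | 13.8 / 11.1 | 49 / 51 | 60 | 60 / 60 |
| 0% | 120 | 31.6 / 27.0 | 73 / 79 | 120 | 120 / 120 |
| 20% | 30 | 22.8 / 22.1 | 29 / 29 | 42.5 | 43 / 42 |
| 20% | 60 | 31.0 / 28.8 | 49 / 51 | 84.9 | 85 / 85 |
| 20% | 120 | 45.2 / 41.5 | 73 / 79 | 169.8 | 170 / 169 |
| 40% | 30 | 42.1 / 41.6 | 29 / 29 | 77.5 | 78 / 78 |
| 40% | 60 | 48.3 / 46.6 | 49 / 51 | 155.1 | 156 / 154 |
| 40% | 120 | 58.9 / 56.1 | 72 / 79 | 310.2 | 309 / 310 |

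Consistency check: with p = 20%, m = 60 and a 10-month treatment median, the share without an end date should be 0.20 + 0.80 × 0.138 = 0.310, as found.

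A second simulation used treatment medians of 150 and 300 days (capped at day 701) and recording to 90 days after last dose. For m = 60 it gave 45.9 and 49.5 days against 84.8 with 20% permanent, and 45.6 and 49.4 against 155.3 with 40%. For m = 120 with none permanent it gave 63.5 and 73.9 against 120.

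The median among events with an end date does not respond to the permanent share, as the selection argument predicts. Kaplan-Meier recovers the all-event median here because the simulation makes censoring independent and contains no deaths. It shows where the bias comes from; it does not show that Kaplan-Meier with death censored would be right in this trial.

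**The case against.** A reader might go further and infer that permanent toxicities vanish from the AESI reporting and that the trial will overstate reversibility. The documents do not support that. The same SAP section says "Additional summaries of the above-mentioned grouped AE categories will include number (%) of patients who have" an event in several categories, one of which is "At least one AESI/AEPI presented by outcome". That table is required and needs no end date. Outcome is on the protocol 8.3.4 list that opens "The following variables will be collected for each AE". Unresolved events also count in the maximum-grade tables and in the required summaries of AESI/AEPI needing endocrine treatment, immunosuppressants or corticosteroids, and they stay in the listings. If anything, the by-outcome table errs the other way: an event that resolves after recording stops stays there as not resolved.

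Four further objections carry weight.

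- Recording may not stop as sharply as Table 2 suggests. Protocol 8.3.3 also calls for follow-up to resolution or stabilization and lets the sponsor ask for more information, and 8.4.1 requires follow-up reports on serious events without an end date. Some late-resolving serious events may therefore acquire an end date.
- The largest gaps compare duration among resolvers with time to resolution over all events, which are different quantities. The rows with no permanent events isolate the bias itself; it is still about 50 against 60 and 73–79 against 120 days.
- A reader might also infer that durations cannot be compared between arms because treatment length differs. Doubling the treatment median moved the figure by only 3.6 days (45.9 to 49.5) or 10.4 days (63.5 to 73.9), and the SAP treats safety summaries as descriptive. The main fault is understatement within each arm.
- The reversibility language describes earlier studies. The overall benefit/risk statement in protocol 2.3.3 does not rely on it.

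None of this repairs the duration table. The by-outcome table counts patients and has no time axis: an event that began a week before recording stopped looks the same as one that had lasted 18 months.

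**Conclusion.** The point holds for the duration summary and no further. Followed as written, that output conditions on resolution within a limited recording window, so it understates duration and cannot reveal persistent toxicity. The companion summaries that would warn the reader are optional and leave out AEPIs.

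The direction follows from the text. The size does not, because the documents give neither AESI durations nor permanent shares. On the stated assumptions it runs from negligible (30-day events, none permanent) to a median that misses most of the all-event figure when events are long or often permanent. This is a modest, cheaply corrected weakness in a committed safety output. The figure should not be read alone.

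**What to change.** Change SAP 4.2.13.1 only.

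- For all AESI/AEPI, including those without an end date, present time from onset to resolution by arm, per patient, for the first event in each grouped term. Censor unresolved events at the earlier of last AE assessment or DCO, and treat death as a competing event. Report cumulative incidence of resolution, for example at 3 and 6 months, and the median where reached. Censoring at death would treat a fatal event as if it could still have resolved.
- Print the number of events without an end date beside the existing duration table.
- Make the ongoing-at-death and ongoing-at-DCO summaries required rather than optional, and include AEPIs.

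All of this uses data already collected. The cost is one program and one table, and duration figures that will look less favourable.

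No change to protocol 8.3.3 is proposed. Recording resolution after Week 12 would need an amendment and would add adverse event ascertainment to contacts that serve survival and subsequent therapy, some of them made by telephone with relatives.

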4.2.13.2 Laboratory assessments

Summaries of laboratory assessments will include the variables listed in Tables 8, 9 and 10 of the CSP (Version 4, 13 November 2020). Calculated creatinine clearance values reported by the site (e.g. at the screening visit) will be summarized separately from programmatically derived CrCl.

Data obtained up until the 90 days following discontinuation of study treatment or until the initiation of the first subsequent therapy following discontinuation of study treatment (whichever occurs first) will be used for reporting. This will more accurately depict laboratory toxicities attributable to study treatment only as a number of toxicities up to 90 days following discontinuation of the study treatment are likely to be attributable to subsequent therapy.

However, to assess the longer-term toxicity profile, summaries of laboratory data may also be produced containing data collected up until 90 days following discontinuation of the study treatment. Any data post 90 days last dose will not be summarized.

Data summaries will be provided in preferred units.

Scatter plots (shift plots) of baseline to maximum value/minimum value (as appropriate) on treatment (i.e. on-treatment is defined as data collected between the start of treatment and the relevant follow-up period following the last dose of study treatment) may be produced for certain parameters if warranted after data review.

For continuous laboratory assessments, absolute value and change from baseline will be summarized using descriptive statistics at each scheduled assessment time by actual treatment group.

Shift tables for laboratory values by worst CTCAE grade will be produced, and for specific parameters separate shift tables indicating increased and decreased directionality of change will be produced. The laboratory parameters for which CTCAE grade shift outputs will be produced are:

- Hematology: Hemoglobin increased and decreased, Leukocytes increased and decreased, Absolute Lymphocyte Count - increased and decreased, Absolute Neutrophils Count - decreased, Platelets - decreased
- Clinical chemistry: ALT increased, AST increased, ALP increased, Total bilirubin increased, Albumin increased, Magnesium increased and decreased, Sodium –

increased and decreased, Potassium – increased and decreased, Corrected calcium – increased and decreased, Glucose – increased and decreased, Creatinine - increased

Additional summaries will include a shift table for urinalysis (Bilirubin, Blood, Glucose, Ketones, Protein) comparing baseline value to maximum on-treatment value.

Liver enzyme elevations and Hy's law

The following summaries will include the number (%) of patients who have:

- Elevated ALT, AST, and Total bilirubin during the study
 - ALT $\geq 3x \leq 5x$, $> 5x \leq 8x$, $> 8x \leq 10x$, $> 10x \leq 20x$, and > 20x Upper Limit of Normal (ULN) during the study
 - AST $\ge 3x \le 5x$, $> 5x \le 8x$, $> 8x \le 10x$, $> 10x \le 20x$, and > 20x ULN during the study
 - Total bilirubin $\ge 2x \le 3x$, $\ge 3x \le 5x$, $\ge 5x$ ULN during the study
 - ALT or AST $\ge 3x \le 5x$, $> 5x \le 8x$, $> 8x \le 10x$, $> 10x \le 20x$, > 20x ULN during the study
 - ALT or AST ≥3x ULN and Total bilirubin ≥2x ULN during the study (Potential Hy's law): The onset date of ALT or AST elevation should be concurrent or preceding the date of Total Bilirubin elevation
- Narratives will be provided in the CSR for patients who have ALT ≥ 3x ULN plus Total bilirubin ≥ 2x ULN or AST ≥ 3x ULN plus Total bilirubin ≥ 2x ULN, where the onset date of ALT or AST elevation should be concurrent or preceding the date of Total Bilirubin elevation.

Liver biochemistry test results over time for patients with elevated ALT or AST (i.e. $\geq 3x$ ULN), and elevated Total bilirubin (i.e. $\geq 2x$ ULN) (at any time) will be plotted. Individual patient data where ALT or AST (i.e. $\geq 3x$ ULN) plus Total bilirubin (i.e. $\geq 2x$ ULN) are elevated at any time will be listed also.

Plots of ALT and AST vs. Total bilirubin by treatment group will also be produced with reference lines at 3×ULN for ALT, AST, and 2×ULN for Total bilirubin. In each plot, total bilirubin will be in the vertical axis.

Plots of ALT, AST, ALP and Total bilirubin, baseline vs. maximum observation on treatment by treatment group will also be produced. Plots will be repeated removing any outliers, as defined by the medical team.

Assessment of thyroid function test results

For the thyroid function tests (TSH, T3 and T4), will be based on data up to 90 days after the last dose of study medication or date of initiation of subsequent therapy (whichever occurs first).

Absolute value and change from baseline will be summarized using descriptive statistics at each scheduled assessment time point by actual treatment group.

Shift tables showing baseline to maximum and baseline to minimum will also be produced for TSH, T3 and T4.

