#### 2.3.2.3 Tremelimumab

Risks with tremelimumab monotherapy include, but are not limited to, GI effects (colitis, diarrhea, enterocolitis, and intestinal perforation); endocrine disorders (hypo- and

hyperthyroidism, hypophysitis, and adrenal insufficiency); skin effects (rash and pruritus); clinical manifestations of pancreatitis (elevations in lipase and amylase); hepatic events (including immune mediated hepatitis and liver enzyme elevations); pneumonitis and ILD; neurotoxicity (including encephalitis, encephalopathy, peripheral motor and sensory neuropathies, and Guillain-Barré syndrome); thrombocytopenia, anemia, and neutropenia; infusion-related reactions and hypersensitivity/anaphylactic reactions; renal events (including tubulointerstitial nephritis/autoimmune nephritis and acute kidney injury, autoimmune arthritis, Sjogren's syndrome, giant cell temporal arteritis and ulcerative colitis); hyperglycemia and diabetes mellitus.

For information on all identified and potential risks with tremelimumab, please always refer to the current version of the tremelimumab IB.

In monotherapy clinical studies, AEs reported at an incidence of  $\geq$  20% include events such as diarrhea, nausea, fatigue, pruritus, decreased appetite, rash, vomiting and dyspnea. Approximately 16% of patients experienced an AE that resulted in permanent discontinuation of tremelimumab, and approximately 45% of patients experienced an SAE. Please see the current version of the IB for a detailed summary of monotherapy data, including AEs, SAEs, and CTC Grade 3 to 5 events reported across the tremelimumab program.

A detailed summary of tremelimumab monotherapy AE data can be found in the current version of the tremelimumab IB

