## Table 8 Clinical chemistry

Albumin	Lipase b
Alkaline phosphatase	Magnesium c
ALT a	Potassium
Amylase b	Sodium
AST a	Total bilirubin a
Bicarbonate c	Total protein
Calcium	TSH d
Chloride c	T3 free e (reflex)
Creatinine	T4 free e (reflex)
Gamma glutamyltransferase c	Urea or blood urea nitrogen, depending on local practice
Glucose	

Lactate dehydrogenase

- Tests for ALT, AST, alkaline phosphatase, and total bilirubin must be conducted and assessed concurrently. If total bilirubin is ≥2 × upper limit of normal (and no evidence of Gilbert's syndrome), then fractionate into direct and indirect bilirubin.
- It is preferable that both amylase and lipase parameters are assessed. For sites where only one of these parameters is routinely measured, either lipase or amylase is acceptable.
- Bicarbonate (where available), chloride, creatinine clearance, gamma glutamyltransferase, and magnesium testing are to be performed at baseline, on Day 1 (unless all screening laboratory clinical chemistry assessments are performed within 3 days prior to Day 1), and if clinically indicated.
- If TSH is measured within 14 days prior to Day 1 (first infusion day), it does not need to be repeated at Day 1.
- Free T3 or free T4 will only be measured if TSH is abnormal or if there is a clinical suspicion of an AE related to the endocrine system.
- AE Adverse event; ALT Alanine aminotransferase; AST Aspartate aminotransferase; TSH Thyroid-stimulating hormone.

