#### **8.3.7** Adverse events based on examinations and tests

The results from the Clinical Study Protocol mandated laboratory tests and vital signs will be summarized in the Clinical Study Report (CSR). Deterioration as compared to baseline in protocol-mandated laboratory values and vital signs should therefore only be reported as AEs if they fulfill any of the SAE criteria or are the reason for discontinuation of treatment with the IP.

If deterioration in a laboratory value/vital sign is associated with clinical signs and symptoms, the sign or symptom will be reported as an AE, and the associated laboratory result/vital sign will be considered as additional information. Wherever possible, the reporting Investigator uses the clinical term, rather than the laboratory term (eg, anemia versus low hemoglobin value). In the absence of clinical signs or symptoms, clinically relevant deteriorations in non-mandated parameters should be reported as AE(s).

Deterioration of a laboratory value that is unequivocally due to disease progression should not be reported as an AE/SAE.

Any new or aggravated clinically relevant abnormal medical finding at a physical examination as compared with the baseline assessment will be reported as an AE unless unequivocally related to the disease under study; see Sections 8.3.9 and 8.3.10.

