3.4.2 Laboratory data

Laboratory data will be collected throughout the study, from screening to the follow-up visits as described in the CSP. Blood and urine samples for determination of hematology, clinical chemistry, and urinalysis will be collected as described in Section 8.2.1 of the CSP. For the definition of baseline and the derivation of post baseline visit values considering visit window and how to handle multiple records, derivation rules as described in Section 4.1.2 will be used.

Change from baseline in hematology and clinical chemistry variables will be calculated for each post-dose visit on treatment. CTCAE grades will be defined at each visit according to the CTCAE grade criteria using project ranges as required, after conversion of lab result to corresponding preferred units. The following parameters have CTCAE grades defined for both high and low values: absolute Lymphoctyes, Potassium, Sodium, Magnesium, Glucose and Corrected calcium.

Corrected Calcium will be derived during creation of the reporting database using the following formula:

Corrected calcium = Total calcium (mmol/L) + ($[40 - Albumin (G/L)] \times 0.02$)

Calculated creatinine clearance (CrCl) will be derived according to the Cockroft-Gault formula (using most recent body weight measurement if available, otherwise subsequent weight can be used) (Cockcroft and Gault 1976).

Males:

Creatinine CL =
$$\frac{\text{Weight (kg) x (140 - Age)}}{72 \text{ x serum creatinine (mg/dL)}}$$

Females:

Creatinine CL =
$$\frac{\text{Weight (kg) x (140 - Age)}}{72 \text{ x serum creatinine (mg/dL)}} \times 0.85$$

Absolute values will be compared to the project reference range and classified as low (below range), normal (within range or on limits of range) and high (above range).

The maximum or minimum on-treatment value (depending on the direction of an adverse effect) will be defined for each laboratory parameter as the maximum (or minimum) post-dose value at any time.

Local reference ranges will be used for the primary interpretation of laboratory data at the local laboratory. Project reference ranges will be used throughout for reporting purposes. The denominator used in laboratory summaries of CTCAE grades will only include evaluable patients, in other words those who had sufficient data to have the possibility of an abnormality.

For example:

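### SAP 4.2.13.2 plans no CTCAE-grade shift table for amylase or lipase, and its albumin direction needs checking against CTCAE 4.03

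*SAP*

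**What the plan says.** SAP 4.2.13.2 opens broadly: "Summaries of laboratory assessments will include the variables listed in Tables 8, 9 and 10 of the CSP". Protocol Table 8 contains albumin, amylase and lipase, so all three enter the descriptive laboratory summaries.

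The same section then introduces a narrower list: "The laboratory parameters for which CTCAE grade shift outputs will be produced are". The chemistry parameters on it are ALT, AST, ALP, total bilirubin, albumin, magnesium, sodium, potassium, corrected calcium, glucose and creatinine. Albumin's entry sits in the run "Total bilirubin increased, Albumin increased, Magnesium increased and decreased".

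On grading, SAP 3.4.2 says "CTCAE grades will be defined at each visit according to the CTCAE grade criteria using project ranges as required" and also "The following parameters have CTCAE grades defined for both high and low values: absolute Lymphoctyes, Potassium, Sodium, Magnesium, Glucose and Corrected calcium". Albumin is not among those six.

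On collection, a footnote to Protocol Table 8 says "It is preferable that both amylase and lipase parameters are assessed", and accepts either enzyme where a site routinely measures only one. On risk, Protocol 2.3.2.3 includes "clinical manifestations of pancreatitis (elevations in lipase and amylase" in its tremelimumab list, and Protocol 8.3.12 names pancreatitis as an AESI. On AE reporting, Protocol 8.3.7 says that deteriorations in mandated laboratory values "should therefore only be reported as AEs if they fulfill any of the SAE criteria or are the reason for discontinuation" of treatment, because those values are summarized in the study report.

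**The concern.** Protocol 8.3.7 makes the laboratory summary the intended place for isolated laboratory deteriorations. That works only if the summary shows how many patients reached each grade in each arm. For amylase and lipase the plan commits to no such count, although the protocol itself names their elevation as a risk of one of the study drugs. Other organ systems covered by the AESI list do have laboratory outputs of this kind: ALT, AST and bilirubin by multiples of the upper limit of normal, shift tables for TSH, T3 and T4, and a creatinine grade shift. The pancreas has none.

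For albumin, the worry is that the one direction listed may not be the direction that CTCAE grades.

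**Working it through.** No sample size, power or alpha is involved. The check sets the planned outputs side by side.

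**1. List check.** The chemistry part of the shift-table list in SAP 4.2.13.2 has 11 parameters. Amylase is absent, lipase is absent, and albumin is present as an increase only.

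**2. Does the collection schedule explain the omission?** No. Protocol Table 1 schedules clinical chemistry at screening and at every cycle, and Table 2 schedules it at Day 30, Week 8 and Week 12 after the last dose. A Table 8 footnote restricts magnesium to baseline, Day 1 and when clinically indicated, yet magnesium has grade shift tables in both directions.

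**3. Follow one patient through the outputs.** Take a high-grade lipase rise with no symptoms that meets no SAE criterion and does not lead to discontinuation.

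| Planned output | Does it count this patient by grade and arm? |
|---|---|
| CTCAE shift tables (SAP 4.2.13.2) | No; lipase is not listed |
| Continuous summaries by visit (SAP 4.2.13.2, statistics as in 4.1) | No; quartiles, minimum and maximum appear, but no count by grade |
| Listings (Protocol 9.5.1) | The value is listed but not tabulated |
| AE tables by maximum grade (SAP 4.2.13.1) | No; Protocol 8.3.7 does not make it an AE |
| AESI tables by maximum grade (SAP 4.2.13.1) | No; they count reported AEs, so the same filter applies |
| Review for other significant AEs (SAP 3.4.1) | Only if expert judgement selects it |
| Shift plots (4.2.13.2) and additional safety summaries (4.2.13) | Optional |

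The grade itself is to be derived at each visit under SAP 3.4.2. Only the tabulation is missing.

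**4. Direction check.**

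| Parameter | SAP 3.4.2: graded high and low? | SAP 4.2.13.2 shift direction |
|---|---|---|
| Lymphocytes, potassium, sodium, magnesium, glucose, corrected calcium | Yes | Both |
| Hemoglobin, leukocytes | Not listed | Both |
| Albumin | Not listed | Increased |

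Six parameters agree. Hemoglobin and leukocytes do not. Read at face value, 3.4.2 gives albumin at most one graded direction. Because the two lists already disagree on hemoglobin and leukocytes, 3.4.2 may itself be incomplete. CTCAE 4.03 is not reproduced in the documents, so they cannot settle the albumin direction.

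**5. Illustration of scale.** The documents give no rate of high-grade enzyme elevation. If one assumes 2% to 10% in the combination arm of about 200 randomized patients, that is 0.02 × 200 = 4 to 0.10 × 200 = 20 patients. At those rates this is an upper limit on patients without a committed graded count. Laboratory data use the safety analysis set, which may be smaller, and some of these patients would be reported as AEs.

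**The case against.** A reader might infer that graded enzyme toxicity and low albumin are never reported. The documents do not support that. All three analytes enter the continuous summaries and the listings. Events that meet an SAE criterion or cause discontinuation reach the AE tables by grade, and pancreatitis reaches the AESI tables by grade. Nor is it right that only means and changes are shown: SAP 4.1 includes quartiles, minimum and maximum, so the most extreme value per arm and visit is visible. What is missing is a count of patients by grade.

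A reader might also call this a known toxicity of both active arms. Protocol 2.3.2.3 names enzyme elevation for tremelimumab monotherapy. The durvalumab list in 2.3.2.1 names pancreatitis, not isolated enzyme rises.

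Nor does it follow that low albumin is lost. SAP 3.4.2 requires grading by the CTCAE criteria. If those grade only low albumin, a worst-grade table built that way could show it correctly under a wrong label.

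Finally, no rule in the documents requires a shift table for every Table 8 analyte, safety outputs are descriptive, and further summaries are allowed. That is true, and it keeps the point minor. But an optional summary is not a commitment, and here Protocol 8.3.7 relies on the laboratory summary to carry the information. Sites measuring different enzymes could distort a combined table. That calls for separate tables, not for omission.

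**Conclusion.** The point holds in a limited form. SAP 4.2.13.2 pre-specifies no CTCAE-grade shift table for amylase or lipase, and no other committed output counts patients by grade and arm for an isolated rise in either. This rests on reading the list as complete, as its introduction implies, and on sites applying Protocol 8.3.7 as written.

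The albumin entry is a query, not a proven error. If CTCAE 4.03 grades only low albumin, the planned table is either empty or mislabelled.

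The consequence is confined to descriptive safety reporting. How many patients it touches cannot be derived from the documents, and the 4 to 20 above depends wholly on an assumed rate. No efficacy analysis is affected.

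**What to change.** In SAP 4.2.13.2:

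- Add amylase (increased) and lipase (increased) to the CTCAE shift-table list. Present them as two separate tables, by actual treatment group in the safety analysis set, with an evaluable-patient denominator for each enzyme. The evaluability rule already in SAP 3.4.2 serves for this.
- Check the albumin entry against CTCAE 4.03 and change it to the direction graded there (decreased, if confirmed).
- Align the directionality lists in 3.4.2 and 4.2.13.2, including hemoglobin and leukocytes.

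The cost is SAP wording and about three descriptive tables. The data are already collected and the grades are already to be derived at each visit.
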